## 5.7 Study Endpoints

Consistent with the study objectives, the primary endpoints will focus on the safety and tolerability of AVT001 treatment versus placebo.

The primary endpoints are:

- (a) The incidence of treatment-emergent adverse events (TEAEs).
- (b) Changes from baseline in clinical laboratory parameters.
- (c) The incidence and severity of local IV-site reactions.
- (d) Changes from baseline in vital signs and electrocardiograms.
- (e) Incidence of severe hypoglycemic events.

Secondary objectives focus on the CD8+ T-cell regulatory system and therapeutic outcomes associated with T1D. These pharmacodynamic effects of AVT001 will be assessed in an exploratory manner.

Secondary endpoints will include:

- (a) Assessment of the HLA-E-restricted CD8+ T cell regulatory activity (“potency assay”)
- (b) Changes from baseline in the area under the curve (AUC) of the stimulated C-peptide levels over the first 4 hours of a mixed meal tolerance test (MMTT)
- (c) Changes from baseline in HbA1c
- (d) Change from baseline in total daily insulin dose
- (e) Changes from baseline in autoantibody levels

The primary time point for analysis is Month 5, at which point the primary assessment of the study objectives is performed.

## 6 Subject Selection and Withdrawal

### 6.1 Inclusion Criteria

Subjects who meet *all* of the following criteria are eligible for enrollment as study participants:

1. Diagnosis of type 1 diabetes, within 12 months of first dosing, confirmed by positive lab result for one or more of the following types of autoantibodies:
  - a. Glutamic acid decarboxylase (GAD65)
  - b. Insulinoma associated protein 2 (IA-2, also known as ICA-512)
  - c. Zinc transporter 8 (ZnT8).
2. Age 16 or older and able to provide informed consent/assent.
3. Has a CD8+ T cell defect that is correctable *in vitro* by co-culture with immature dendritic cells loaded with the synthetic oligopeptide from Hsp60sp.
4. If a participant is female with reproductive potential, willing to avoid pregnancy through the duration of the trial.
5. Signed and dated written informed consent/assent.

### 6.2 Exclusion Criteria

Subjects who meet *any* of the following criteria are *not* eligible for enrollment as study participants:

1. Poorly controlled diabetes despite insulin therapy, who in the opinion of the investigator would not be a good candidate for participation in a clinical trial
2. Screening hemoglobin <10.0 g/dL; leukocytes <3,000/uL; neutrophils <1,500/uL; lymphocytes <800/uL; platelets <100,000/uL
3. Screening Urine Albumin Excretion > 300mg/gmCr
4. Screening eGFR < 60 mL/min/1.73m^2
5. Screening ALT or AST > 1.5x upper limit of normal (ULN)
6. Screening bilirubin > 2.0 mg / dL, or > 3.0 mg / dL for participants with Gilbert's Syndrome
7. Current use of immunosuppressive or immunomodulatory therapies, including pharmacologic doses of systemic steroids (topical steroid creams and inhaled steroids without large systemic absorption are allowed).
8. Coincident medical condition likely to require immunosuppressive or immunomodulatory therapies.
9. Coincident medical condition likely to limit short term (5 year) life expectancy (malignancy, symptomatic coronary artery disease, recent stroke)
10. Prior radiation therapy, immunotherapy (within 1 year of screening), or chemotherapy
11. Serologic evidence of current HIV-1 or HIV-2 infection
12. Serologic evidence of hepatitis C infection
13. Serologic evidence of acute or chronic active hepatitis B as measured by Core Ab positive and / or Surface Antibody antigen positive
14. Subjects with other autoimmune conditions (except compensated or treated autoimmune thyroid, celiac, alopecia, or vitiligo diseases)

15. Women who are pregnant (pregnancy testing during screening), breastfeeding, or planning pregnancy during the study period.
16. Inadequate venous access to support leukapheresis.
17. Any condition that in the opinion of the investigator would preclude the subject from participating in a clinical trial.
18. Abnormal screening ECG that in the opinion of the investigator or sponsor would pose a safety risk.

### **6.3 Early Withdrawal of Subjects**

If a subject is discontinued from the study prematurely, the Investigator must select the primary reason for discontinuation on the End of Study eCRF. In addition, every effort should be made to complete the assessments listed under the “Early Term” column on the Schedule of Events.

Subjects withdrawn from the study will be considered evaluable for statistical assessment.

A subject may be removed from the study for the following medical or administrative reasons:

- Adverse Event: If a subject experiences an adverse event that the subject finds unacceptable or that, in the judgment of the Investigator or the Medical Monitor presents an unacceptable consequence or risk to the subject, the subject may be discontinued from further participation in the study.
- Administrative Discontinuation: After consultation with the Investigator or Medical Monitor, a subject may be discontinued from the study for failure to comply with protocol requirements. All instances of noncompliance must be documented in the eCRF.
- Refusal of Assessments: If for any reason, following dosing, the subject refuses further assessment during the study, the subject shall be discontinued from the study and the reasons for refusal documented. Reasonable efforts shall be made to monitor the subject for adverse events following such discontinuation. Such efforts shall be documented.

Standard supportive therapy will be maintained for subjects withdrawn from active treatment. Every effort will be made to collect safety data from these subjects through the end of study.

## 7 Description of Study Drug

A study drug handling manual and study drug administration manual (Manual of Operating Procedures, ie, MOP) describes study drug management in detail. The MOP includes procedures for collection, transport, processing, storage, preparation (for dosing), and administration of study medication, as well as details regarding how the blinding is to be maintained during the infusion process. The following sections provide an overview of the key elements of those activities, but the MOP should be referred to for details.

Drug name and active ingredients: The study drug represents an individualized preparation of autologous immature dendritic cells, derived by culture from the subject's adherent primary monocytes with GM-CSF and IL-4 for 6 days, and loaded passively with the synthetic oligopeptide from Hsp60sp.

Formulation of dosage: AVT001 will be cryopreserved in infusible cryomedia in infusion bags. Each infusion bag will contain between  $7 \times 10^6$  and  $10 \times 10^6$  cells, and each subject randomized to AVT001 will have 3 such bags manufactured for infusion. The cryopreserved cells will be manufactured at the Dana Farber Cancer Institute Cell Manipulation Core Facility (DFCI-CMCF) and will be transported to the investigational site for infusion.

Route of administration: The infusions will be administered intravenously.

Frequency of administration: Three (3) infusions will be administered 30 (+/- 7) days apart. While there is a 7-day window for the infusions, they should occur at least 21 days apart.

Table 2 provides a summary description of the drug products, including the dosage form, the unit dose, and a physical description of the products.

**Table 2: Investigational Product (Protocol AVT001-T1D-01)**

Investigational Product		
Product Name:	AVT001	Placebo
Dosage Form:	20 mL AVT001 suspension with 10% DMSO in Human Serum Albumin	20 mL saline with 10% DMSO in Human Serum Albumin
Packaging:	Cryopreservation bags	Cryopreservation bags
Route of Administration:	Intravenous (i.v.)	Intravenous (i.v.)
Physical Description:	Blinded (covered) bottle/tube	Blinded (covered) bottle/tube
Manufacturer:	DFCI-CMCF	DFCI-CMCF

### 7.1 Administration of Study Drug.

A study drug handling manual and study drug administration manual (Manual of Operating Procedures, ie, MOP) describes study drug management in detail.

Administration of the treatment regimen is as follows:

- On Study Day 1, the subject will receive study treatment (the AVT001 or placebo infusion).
- The interval between injections will be 30 (+/- 7) days. Subsequent injections will be at Study Day 30 and 60 (each ± 7 days and at least 21 days apart), for a total of 3 i.v. injections.

Subjects will be observed for at least 2 hours post-end of each infusion. Safety and tolerability assessments will be performed, including measurement of vital signs. Local tolerability at the infusion site (such as pain, swelling, tenderness, and erythema) will be assessed via adverse event reporting. Please refer to the study drug handling manual and study drug administration manual (Manual of Operating Procedures, ie, MOP) for details on monitoring, Receiving, Storage, Dispensing and Return.

A study drug handling manual and study drug administration manual (Manual of Operating Procedures, ie, MOP) describes study drug management in detail.

## 7.2 Reconciliation of Drug Product

A study drug handling manual and study drug administration manual (Manual of Operating Procedures, ie, MOP) describes study drug management in detail.

## 8 Study Procedures

Study procedures are listed below and can also be found in the Schedule of Events (Table 3). No study procedures will be performed prior to obtaining informed consent.

### 8.1 Informed Consent

The consent process will be conducted by qualified study personnel. All participants (or their legally acceptable representative) must read, sign, and date a consent form prior to participation in the study and/or undergoing any study-specific procedures.

The informed consent form must be updated or revised whenever important new safety information is available, when indicated for a protocol amendment, and/or whenever any new information becomes available that may affect a subject's participation in the study.

### 8.2 Screening/Randomization/Leukapheresis

#### 8.2.1 Screening Study Day ≤ - 90

Screening assessments may be performed at more than one visit, if needed, and must be completed prior to randomization, to establish subject eligibility. Unless otherwise noted, all tests will be required within 90 days prior to treatment.

- Medical history including prior treatment, current medicines, and drug allergies
- Physical exam including blood pressure, pulse, temperature, weight
- Screening Laboratory studies including:
  - Complete Metabolic Panel (CMP) to include: glucose, BUN, creatinine, electrolytes, calcium, total protein, albumin, total bilirubin, AST, ALT, alkaline phosphatase
  - Complete Blood Count with differential (CBC w diff) [CBC may need to be repeated if not performed within acceptable safety timeframe prior to leukapheresis; see MOP]
  - HbA1c
  - eGFR (calculated)
  - Urine MicroAlbumin panel (urine microalbumin, urine creatinine, microalbumin/creatinine ratio)
  - Creatine Clearance (CrCl) (calculated)
- Measurement of auto-antibodies, including:
  - Insulin associated aAb (IAA)
  - Insulinoma associated protein 2 (IA-2, also known as ICA-512)
  - Glutamic acid decarboxylase (GAD65)
  - Zinc transporter 8 (ZnT8).
- Evaluation of HLA-E-restricted CD8+ T cells ("potency assay").
- A urine pregnancy test will be collected for females of child-bearing potential.
- ECG
- Viral studies comprising HIV-1, HIV-2, HBV Core Ab positive and / or Surface Antibody antigen positive, and HCV serology.

- Vein check

### **Screening Lab eligibility requirements**

- Potency Assay results from Screening do not expire.
- Auto-antibody and Viral testing results from Screening expire 6 months from collection.
- All other safety labs results from Screening expire after 90 days from collection including urine pregnancy tests for women of child bearing potential.

### **8.2.2 Randomization**

Upon successful completion of all eligibility requirements, study participants may be randomized to the trial. Each subject will be randomized to treatment in a 2:1 ratio of AVT001:Placebo. As this is a first-in-man study, block sizes of N=3 for the first six subjects will be used to allow for review of the initial six subjects with four AVT001 and two placebo-treated. Thereafter, the block sizes will be randomly assigned to ensure the integrity of the randomization schema while maintaining a 2:1 ratio of AVT001 to placebo.

### **8.2.3 Leukapheresis**

Following randomization, all subjects (including those randomized to placebo arm as well as the AVT001 arm) will undergo leukapheresis according to standard clinical procedures.

The apheresis product will be delivered to Dana Farber Center Cancer Institute (DFCI), Cell Manipulation Core Facility (CMCF) for processing to produce AVT001. Detailed scheduling, coordination, communication, handling, and other procedures for all vein-to-vein operations are described in the MOP.

Leukapheresis is to be performed after randomization, with sufficient time for AVT001/placebo manufacture prior to the end of window between Screening Visit (Visit 1) and first infusion (Study Day 1, Visit 3). Initial manufacture of blinded IP is expected to take a minimum of 28 days.

### **8.3 Double-Blind Treatment Period**

The double-blind treatment period includes 4 scheduled clinic visits. These visits will include study drug administration as well as assessment of safety endpoints.

#### **8.3.1 Study Days 1, 30 ± 7 days, and 60 ± 7 days**

On the first study day, a 4-hour Mixed Meal Tolerance Test (MMTT) will be performed as part of baseline evaluations. The meal test will be performed in the morning after an overnight fast, with no food or drink (with the exception of water). At the outset, a mixed meal, consisting of High Protein Boost will be administered. Blood samples for C-peptide and glucose will be collected at the following timepoints (in minutes, relative to administration of the mixed-meal): -10, 0, 15, 30, and then at 30 minute-intervals until the last time point of 240 minutes.

1-2 days prior to each study day, study personnel will contact the subject to confirm that they remain in generally good health and that there are no symptoms of acute illness.

Prior to dosing on Study Day 1, a review of eligibility should be performed and confirmed. If, prior to dosing, a randomized subject is not suitable (ineligible) for the trial, that subject will be considered a “randomization failure” and will be replaced.

The following procedures will be performed prior to study drug administration on each dosing day:

- Any changes to medical history including prior treatment, current medicines, and drug

- Focused physical exam including blood pressure, pulse, temperature and weight.
- Laboratory studies including:
  - CMP
  - CBC w diff
  - HbA1c
  - Urine MicroAlbumin panel
  - CrCl (calculation)
- 
- Measurement of auto-antibodies, including:
  - Insulin associated aAb (IAA)
  - Insulinoma associated protein 2 (IA-2, previously known as ICA-512)
  - Glutamic acid decarboxylase (GAD65)
  - Zinc transporter 8 (ZnT8).
- A urine pregnancy test will be collected for females of child-bearing potential.
- Any severe hypoglycemic events occurring since the prior study visit will be recorded. Note that non-severe events are not being collected in the database in this study, but will be monitored by the investigator, consistent with the site's standard of care.

Study drug will be administered during these visits. Laboratory data will be collected prior to initiation of the infusion of study drug.

Subjects will be observed for at least 2 hours post-end of each infusion. Safety and tolerability assessments will be performed during and following the infusion, including measurement of vital signs. Vital sign frequency peri-infusion is monitored per the site's standard of care and a recommendation for the minimal frequency is described in the MOP. Local tolerability at the infusion site (such as pain, swelling, tenderness, and erythema) will be assessed via adverse event reporting. Any adverse events or new concomitant medications will be recorded.

### 8.3.2 Study Day 90 ± 7 days

Subjects will return one month after the last infusion for safety and tolerability assessments. This will include a physical exam, insulin usage, vital signs, clinical laboratories CMP, CBC w diff, HbA1c, Urine MicroAlbumin panel, CrCl (calculated), adverse events, and concomitant medications. Local tolerability at the infusion site (such as pain, swelling, tenderness, and erythema) will be assessed via adverse event reporting. Samples for the potency assay and other glycemic measures will be collected.

- Measurement of auto-antibodies, including:
  - Insulin associated aAb (IAA)
  - Insulinoma associated protein 2 (IA-2, previously known as ICA-512)
  - Glutamic acid decarboxylase (GAD65)
  - Zinc transporter 8 (ZnT8).

### 8.4 Long-Term Follow-Up Period

Continued data collection will be performed during the long-term follow-up period. There are 5 planned in-clinic visits during this period.

#### **8.4.1 Study Day 150 ± 7 days**

This visit will include a full assessment of safety, tolerability, and efficacy. This will include a physical exam, insulin usage, vital signs, clinical laboratories CMP, CBC w diff, HbA1c, Urine MicroAlbumin panel, CrCl (calculated) adverse events, and concomitant medications. A urine pregnancy test will be collected for females of child-bearing potential.

Samples for the potency assay and for pancreatic  $\beta$ -cell function (MMTT) and other glycemic measures will be collected.

- MMTT C-Peptide
- Measurement of auto-antibodies, including:
  - Insulin associated aAb (IAA)
  - Insulinoma associated protein 2 (IA-2, previously known as ICA-512)
  - Glutamic acid decarboxylase (GAD65)
  - Zinc transporter 8 (ZnT8).
- Total daily insulin usage over the prior 3-7 days in the immediate period prior to the visit
- Any severe hypoglycemic events occurring since the prior study visit will be recorded.

#### **8.4.2 Study Day 270 ± 14 days, 360 ± 14 days, 540 ± 14 days, and 720/Early Term ± 14 days**

These visits will include a physical exam (can be symptom-driven except at Study Day 360, in which a full physical examination is required), insulin usage, vital signs, clinical laboratories CMP, CBC w diff, HbA1c, Urine MicroAlbumin panel, CrCl (calculated), adverse events, and concomitant medications. A urine pregnancy test will be collected for females of child-bearing potential at the Study Day 720/Early Term visit only.

Samples for the potency assay will be collected, and samples for pancreatic  $\beta$ -cell function will be collected.

- MMTT C-Peptide (MMTT will not be performed at the Day 270 visit, but will be collected at Day 360, 540, and 720/Early Term visits).
- Measurement of auto-antibodies, including:
  - Insulin associated aAb (IAA)
  - Insulinoma associated protein 2 (IA-2, previously known as ICA-512)
  - Glutamic acid decarboxylase (GAD65)
  - Zinc transporter 8 (ZnT8).
- Total daily insulin usage over the 3-7 days in the immediate period prior to the visit
- Any severe hypoglycemic events occurring since the prior study visit will be recorded.

#### **8.5 ECGs**

All scheduled ECGs will be performed after the subject has rested supine for approximately 5 minutes. ECGs will be collected during Screening and Day 90 ± 7 days

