### 5.6.1 Stopping Rules

Subjects will be clinically evaluated for evidence of toxicity from  $\geq$  grade 3 toxicity as determined by CTCAE which is unmanageable, unexpected and (possibly, probably or definitely) related, and attributable to protocol therapy. Termination of enrollment would be considered with 2 dose limiting toxicities (DLTs) in the first 6 evaluable subjects and 3 in the first 9 evaluable subjects. In the event of a DLT for a given subject, doses will be discontinued, the subject clinically evaluated, and taken off study. The study will be stopped for DLT resulting in death of a subject.

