## 17.5. ECG EVALUATIONS

The following electrocardiogram (ECG) parameters will be measured for this study as per the schedule of events (refer to protocol, Table 3):

- PR interval (msec)
- RR interval (msec)
- QRS interval (msec)
- QT (uncorrected) interval (msec)
- Overall ECG evaluation (Investigator's judgment)
  - Normal
  - Abnormal, not clinically significant (NCS)
  - Abnormal, clinically significant (CS)

The following summaries will be provided by treatment group based on the SAF analysis population for each ECG parameter:

- Observed and change from baseline by visit (for quantitative parameters)
- Number and percentages of subjects with at least one markedly abnormal post-baseline observed value/change from baseline (for quantitative parameters; refer to [Section 17.5.11](#))
- Shift from baseline in overall ECG interpretation to the worst post-baseline assessment

All ECG data will be listed. ECG results meeting one of the markedly abnormal criteria in Section 17.5.1 will be identified.

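### The only scheduled post-dose ECG is at Day 90 and the Early Term visit has none, so the ECG component of primary endpoint (d) may be missing for subjects who leave before then

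*Combined protocol and SAP*

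**What the plan says.** Protocol Amendment 3, section 5.7, lists among the primary endpoints "Changes from baseline in vital signs and electrocardiograms". On timing, section 8.5 says "ECGs will be collected during Screening and Day 90 ± 7 days", and the ECG row of Table 3 is marked at Screening and Day 90 only.

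For a subject who discontinues, section 6.3 says that "every effort should be made to complete the assessments listed under the “Early Term” column on the Schedule of Events". Section 8.4.2 describes that visit: after the physical exam it names "insulin usage, vital signs, clinical laboratories CMP, CBC w diff, HbA1c, Urine MicroAlbumin panel, CrCl (calculated), adverse events, and concomitant medications", and goes on to the potency assay, MMTT, autoantibodies, insulin use and severe hypoglycemia. It names no ECG, and neither does the Early Term column of Table 3. For DLTs, section 5.6.1 says: "In the event of a DLT for a given subject, doses will be discontinued, the subject clinically evaluated, and taken off study". Again no ECG is named.

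SAP v2.0, section 17.5, summarises ECGs on the safety population: observed value and change by visit, a shift to the worst post-baseline interpretation, and "Number and percentages of subjects with at least one markedly abnormal post-baseline observed value/change from baseline". It does not say how a subject with no post-baseline ECG is handled.

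**The concern.** A subject who receives one or two infusions and then leaves the study has been exposed and belongs to the safety population, but the protocol requires no ECG from that subject after dosing. Section 6.3 says that withdrawn subjects count as evaluable and sends them to a visit that yields no ECG data.

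Some of these exits are related to safety. Section 6.3 lists adverse events as a reason for removal, and section 5.6.1 takes a subject with a DLT off study. The ECG results would then come mainly from subjects who tolerated treatment long enough to reach Day 90. In a first-in-man trial whose primary objective is safety and tolerability, that selection favours a finding of no ECG effect. As section 17.5 is written, the report need not show how many subjects the finding leaves out.

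**Working it through.** **1. The plan's own figures (protocol 9.2, SAP 7.1).** With 14 AVT001 subjects and a true incidence of 12%, the chance of at least one event is 1 − (1 − 0.12)^14 = 0.833, which meets the stated 80% or more. Inflating 21 for 10% dropout gives 21 / 0.9 = 23.3, rounded up to 24, or 16 on AVT001 and 8 on placebo. Both figures reproduce.

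**2. Required assessments for a subject who leaves between the first infusion and Day 90.**

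| Component of endpoint (d) | Required after dosing and before exit | Required at Early Term |
|---|---|---|
| Vital signs | Yes, during and after each infusion (8.3.1) | Yes (8.4.2, Table 3) |
| ECG | None (8.5, Table 3) | None (8.4.2, Table 3) |

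A subject who stops dosing but stays in the study still reaches the Day 90 ECG. The gap concerns subjects who leave the study.

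**3. How many subjects.** The plan allows 10% dropout before the Month 5 (Day 150) assessment and gives no split by time, so the share before Day 90 is an assumption.

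- Constant hazard to Day 150: 1 − 0.9^(90/150) = 0.061. Of 24 subjects, 0.061 × 24 = 1.5. Of 16 on AVT001, 0.061 × 16 = 1.0.
- All dropout before Day 90 (upper end): 0.10 × 24 = 2.4. On AVT001, 0.10 × 16 = 1.6, or roughly 2.
- No dropout before Day 90 (lower end): 0.

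**4. Effect on the chance of seeing a 12% ECG abnormality on AVT001.** With 16 subjects assessed: 1 − 0.88^16 = 87.1%. With 15: 85.3%. With 14: 83.3%. The loss is at most about 4 percentage points, and the result stays above the stated 80%. This treats the missing subjects as typical of the arm, which is the doubtful part when they leave for poor tolerability.

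**5. What the SAP does with an ECG taken at exit.** SAP 6.3 keeps unscheduled and early termination measurements out of by-visit summaries. It says only that they may contribute to a maximum value where one is needed, with a shift table as its example. An exit ECG could therefore enter the worst-value shift table and, on the wording of 17.5, the count of markedly abnormal values, but not the by-visit change table.

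**6. Denominator.** Protocol 9.7 limits descriptive statistics for laboratory tests, ECGs and vital signs to subjects with both baseline and on-treatment values. SAP 17.5 names the safety population for its ECG counts and states no separate denominator for the percentages.

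**The case against.** The strongest reply is that the gap is narrow and partly covered. Section 6.3 calls for best efforts to collect safety data from withdrawn subjects to the end of the study. A subject with a DLT is clinically evaluated, which may well include an ECG. A clinically significant ECG finding would be recorded as an adverse event (11.1.2) and so reach endpoint (a). SAP 6.3 leaves room for an unscheduled ECG in the worst-value tables. Not all dropout is for safety, since section 6.3 also lists noncompliance and refusal. Losing two AVT001 subjects leaves 14, the number the trial was sized on. All of this stands and limits the size of the point. None of it requires a post-dose ECG in a subject who leaves early, or makes the number without one visible.

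Three stronger readings are tempting, and the documents do not support them:

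- **Early leavers cannot be scored on endpoint (d) at all.** They can be scored on vital signs, which are taken from the first infusion and analysed separately (SAP 17.4).
- **Unassessed subjects would be counted as having no abnormality, hiding true cases in a denominator of 16.** The denominator for the ECG percentages is not stated, and protocol 9.7 points to subjects with data. A specific count of hidden cases would also need every missing subject to be on AVT001, to have an abnormal ECG and to have no unscheduled ECG.
- **The stopping rule would let DLT subjects leave without review.** Section 5.6.1 already considers ending enrolment at 2 DLTs in the first 6. The investigator and medical monitor review each of the first 6 subjects (5.5), and the DSMB reviews unblinded data after 3, 6 and 15 (5.6).

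**Conclusion.** The point holds for the ECG component of endpoint (d) only. A subject who leaves before Day 90, including one taken off study for a DLT, has no required post-dose ECG. Unscheduled ECGs or safety follow-up could fill the gap but are not mandated.

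Under the planned dropout this concerns about 1.5 of 24 subjects if the hazard is constant to Day 150, and at most about 2.4 of 24, or roughly 2 of 16 on AVT001. Both figures rest on the planned 10% and an assumed time split; actual dropout is not given in the documents. The loss of precision is minor. The reason to act is that the missing subjects are partly selected for poor tolerability. The direction of any bias is towards no ECG effect; the documents do not allow its size to be estimated.

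**What to change.** **Protocol 8.5 and Table 3:** state that the Day 90 ECG is performed at the Early Term visit for any subject who leaves before Day 90.

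**SAP 17.5:**
- State that this ECG counts in the table of subjects with at least one markedly abnormal value and in the shift to the worst post-baseline interpretation. At present SAP 6.3 only allows that it may. It would stay out of the by-visit change table under SAP 6.3, which is reasonable because its timing differs.
- Use subjects with at least one post-baseline ECG as the denominator, consistent with protocol 9.7.
- Report by arm the number in the safety population with no post-baseline ECG.

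**Cost:** one entry in Table 3 with a matching line in 8.5, and a few sentences in the SAP. The ECG is one already planned, done at a visit the subject is already asked to attend. The downside is that its interval from dosing differs from Day 90 in those few subjects.

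**What can still be done:** SAP v2.0, section 4.2, records that the primary analysis followed the last subject's Month 5 visit, with data locked on 29 April 2022. The schedule change can no longer recover an ECG in this trial and is of use only for a later protocol. The denominator and missing-count changes need no new data. They can be applied at the Month 12 supplemental analysis (4.3) and at the final analysis, before which section 4.4 already plans a SAP amendment.
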